Description of Study Site. The proposed study will recruit from the ED in the VA Ann Arbor Healthcare System (VAAAHS). The following numbers are based on data from 2015. This ED treated a total of 10,653 patients drawn from a relatively wide geographic area that included western Wayne County (Detroit area), as well as several mid-sized cities and rural communities. Patients seen had the following characteristics: 9% female; 75% White, 10% African American, and 3% of another race (mainly multiple races); about 2% Hispanic. The VAAAHS ED is very supportive of this research project. Only one site will be included in this study to enhance our ability to ensure fidelity of peer-delivered intervention content through closer supervision and monitoring. If shown to be efficacious, we will scale up in order to add many sites later through an implementation study.

Inclusion Criteria for Screening. (1) adults age 18 years of age or older presenting for care in the Ann Arbor VHA ED; and (2) medically stable and able to provide informed consent per Mini-Cog assessment score of 3 or more.

Inclusion Criteria for the RCT. *Individuals will be eligible to participate in the RCT if they: (1) have an AUDIT-C score of 4 or more for men and 3 or more for women in the prior 3 months, indicating that they meet criteria for hazardous use⁵⁵; and 2) have a telephone and/or the ability to provide information about individuals who can help contact the participant. Homeless Veterans may not have a telephone but will be asked for individuals who can help to contact them (e.g. shelter, family, friends, etc.). Importantly, the study will include not only those with less severe hazardous drinking but also those with more harmful use and severe problems to address the problems and needs of Veterans who can most benefit from linkage to primary and secondary care. Furthermore, a recent study validates the full AUDIT among Veterans, with scores of 14 and 10 (male, female, respectively) indicating an AUD.⁵⁶ However, to be inclusive and sure that all Veterans who may need specialty care have the information to get to that care, we will set scores for specifically recommending specialty care to the Veteran participant more conservatively at 10 for men and 8 for women.* Both study conditions will receive information on accessing VHA primary/specialty services.

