Recruitment / Informed Consent. Veterans will be recruited at the VAAAHS ED. The study will involve a 2-stage consent process utilized in our prior ED research, providing separate verbal consent with waived documentation for the screening, and written consent for the randomized trial. All who screen positive on the AUDIT-C, agree to participate, and sign consent forms will be enrolled. They will receive a baseline assessment as described in the measures. Participants may have the option to complete paper-form alone, or within up to 2-weeks after enrollment if necessary. *Research staff will recruit, obtain consent, and participants will self-administer the screening and assessment questions. The peers will shift in the ED to deliver the brief advice with supervision from the research supervisor, likely a social worker who is a Licensed Independent Practitioner.*

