ED Staffing / Subject Accrual. Because it is not possible to staff the project continuously (168 hours/week), this study will use the following sampling frame that has been used successfully in our previous ED research to ensure obtaining a representative sample of Veterans presenting to the AAVA ED. Project staff in the ED will recruit patients for the study 5 days per week between the hours of 10AM to 6PM. The majority of the recruitment time will be spent in the ED between 10AM and 6PM because 65-70% of patients enter the ED during those hours. In addition, another three days/week will include a weighted sampling of recruiting between either 7AM-3PM or 3PM-11PM time period. Thus, a total of 8 shifts (8 hours each) will be staffed each week to recruit, consent, screen patients, conduct baseline assessments, and deliver brief advice. Based on our previous ED studies where we have used similar staffing schedules we expect to accrue the following numbers: 30 months of screening x ~130 patients/month approached = 3,900; it is expected that 80% (n=3,120) will agree to participate and will be screened. We conservatively expect that 15% of the screened patients will have a positive screen and will be randomized (450 randomized; 225 per group). Randomization Procedures. Stratified random assignment to conditions will be by sex and presence of an AUD (yes/no) defined as a score of 14 for men and 10 for women on the AUDIT. Randomization by sex will be used because men and women generally differ in their rates and nature of alcohol use, problems, and outcomes. Random assignment will also be stratified based on meeting criteria for past year AUD (yes/no) because of potential differences in problem severity and potential intervention response. Randomization will proceed in blocks of 10 within study cells, in order to equalize randomization over time. Follow-up staff will be blind to condition. Participants in both conditions will receive written information regarding alcohol and VHA resources and be re-contacted to complete 3-, 6-, and 12-months follow-ups.

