Brief Advice Condition. Participants assigned to BA will receive brief alcohol advice from a research assistant. Content is comparable in intensity and scope to the current computer protocol that is required to be used in VHA primary care, and a health pamphlet with VHA and community resources and information about alcohol use and other issues. Those randomized to the BA condition will receive no post-ED sessions, consistent with

program offered by the National Alliance on Mental Illness (NAMI) consists of 10 two-hour sessions including topics such as stigma, self-disclosure, disorder-specific information, suicide prevention, and recovery.⁵⁸ Online training is also available through the New England MIRECC Peer Education Center. Peer mentors will be trained by experienced investigator trainers ([name], [name], [name]) in alcohol issues, intervention content, linkage in primary and specialty care. The investigators will refine the peer intervention delivery manual.

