We expect that 15% of the screened patients will have a positive screen and will be randomized, yielding 225 per group (total=450). Based on data from the study site, we anticipate the gender composition of the sample to be approximately 7.5% female and 92.5% male; we expect the following racial composition of the sample: approximately 20% African American, 75% Caucasian, and 5% other (i.e., Asian, American Indian, Native Hawaiian or Other Pacific Islander). We also expect that 1-2% of adults will identify as Hispanic ethnicity.

Inclusion criteria for screening. 1) adult Veterans age 18 years of age or older presenting for care in the VAAAHS ED; 2) medically stable and able to provide informed consent.

Inclusion criteria for the RCT. Individuals will be eligible to participate in the RCT if they: (1) have an AUDIT-C score of 4 or more for men and 3 or more for women in the prior 3 months, indicating that they meet criteria for hazardous use (NIAAA 2005; World Health Organization); 2) a telephone and/or the ability to provide information about individuals who can help contact the participant. Importantly, the study will include those with more severe problems to address the problems and needs of Veterans who can most benefit from linkage to primary and secondary care. The more severe users will receive content that actively encourages treatment initiation.

Exclusion criteria for screening. (1) patients who do not understand English; (2) prisoners; (3) current or recent substance use treatment in past 3 months; (4) patients currently in or having received peer services in the past 3-months per medical record; (5) pregnant women; (6) patients deemed unable to provide informed consent as stated above; and (7) profound psychotic symptoms and/or cognitive deficits that would prevent patients from understanding the content of the intervention and/or assessments.

It has been our experience that some patients are unable to provide informed consent on entry to the ED (e.g. psychotic symptoms; acute intoxication) but that their status will improve sufficiently prior to ED discharge to make them eligible to be approached by research staff. Participants may be excluded at the discretion of the Principal Investigator based on participant or study staff best interest (e.g., if participant should become physically or verbally aggressive towards study staff, or if the study staff know a patient or their family

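### The single fixed block size of 10 lets up to one allocation in six be known in advance to someone who tracks a cell; randomly varied sizes would cut this to about 6%

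*Combined protocol and SAP*

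**What the plan says.** - **Block rule.** Randomization Procedures: "Randomization will proceed in blocks of 10 within study cells". No variation in size is mentioned. The cells are sex by AUD, with AUD defined by an AUDIT cut-off.
- **Size and ratio.** ED Staffing / Subject Accrual plans "450 randomized; 225 per group", so each block of 10 holds five of each arm.
- **Setting.** Description of Study Site: "Only one site will be included in this study".
- **Recruiters and order of events.** Recruitment / Informed Consent: "Research staff will recruit, obtain consent". Under Measures, the screen collects demographics and the full AUDIT, so a patient's cell can be known before written consent to the trial. The Human Subjects section places randomization after written consent and baseline. Baseline may be deferred by up to two weeks.
- **Who delivers the Brief Advice (BA) session.** Brief Advice Condition: "Participants assigned to BA will receive brief alcohol advice from a research assistant". Potential Risks agrees. The Alcohol BIs background describes the comparator as clinician advice, the Human Subjects section names an ED clinician or the peer mentor, and the recruitment section has peers giving the advice without limiting this to one arm.
- **Masking and concealment.** Follow-up staff are to be blind to condition. The plan does not say who holds the list, how an assignment is released, or whether recruiters are kept from knowing the block size.

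**The concern.** Every block of a fixed, known size must end in balance, so its last allocations can be worked out from the first ones. Randomizing after consent and baseline prevents a reaction to a revealed assignment. It does not prevent prediction of the next one. A recruiter who expects a particular arm could press harder or less hard for consent from a patient whose screening result is already known. That would make the arms differ in ways linked to prognosis or motivation.

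Several features make tracking feasible here. There is one site, and nearly all participants fall in the two male cells. On one reading of the plan, research staff give the BA session themselves and so see who is assigned to it.

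**Working it through.** The plan gives no figure for predictability, so there is none to reproduce.

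**Inputs.** Block size 10 and 1:1 allocation, N = 450, four cells (Randomization Procedures and ED Staffing / Subject Accrual); 7.5% women (Human Subjects); 30 months of screening (ED Staffing / Subject Accrual).

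**1. Determined allocations in a block of 10.** There are C(10,5) = 252 balanced blocks. Place k is determined if one arm already has its five among the first k − 1 places. The probability is 2 × C(k − 1, 5) / 252.

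| Place | Calculation | Probability |
|---|---|---|
| 1 to 5 | none possible | 0 |
| 6 | 2 × 1 / 252 | 0.8% |
| 7 | 2 × 6 / 252 | 4.8% |
| 8 | 2 × 21 / 252 | 16.7% |
| 9 | 2 × 56 / 252 | 44.4% |
| 10 | 2 × 126 / 252 | 100% |

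The sum is 420 / 252 = 1.667 per block, or 16.7%. With 45 complete blocks this is 45 × 1.667 = 75 of 450. Simulating incomplete last blocks in four cells gives about 72 of 450 (16.1%). The AUD share is not given; assuming 30% to 70% hardly changes the result, nor does 9% women in place of 7.5%.

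**2. Best guess.** Always naming the arm with more places left is right in [5 + (1024/252 − 1)/2] / 10 = 6.53 / 10 = 65.3% of allocations.

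**3. Incomplete sight.** Suppose each earlier allocation is seen with probability q and the block position is known. Certainty then needs all five of the exhausted arm to have been seen, so the share is q⁵ / 6:
- q = 0.90: 0.590 / 6 = 9.8%
- q = 0.75: 0.237 / 6 = 4.0%
- q = 0.50: 0.031 / 6 = 0.5%

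**4. Pending recruits.** If one earlier recruit in the cell is always awaiting baseline, the probabilities in step 1 shift by one place: (0.8 + 4.8 + 16.7 + 44.4) / 10 = 6.7%. With two always pending, (0.8 + 4.8 + 16.7) / 10 = 2.2%.

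**5. How many sequences there are to follow.** 450 / 30 = 15 randomizations a month. The plan expects a sample "approximately 7.5% female and 92.5% male", so 0.925 × 15 = 13.9 a month fall in the two male cells. About 34 women (0.075 × 450) are spread over the other two.

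**6. Mixed sizes 8, 10 and 12, equally likely.** Take an observer who knows the possible sizes and where each block starts, but not its size. That observer can be certain only once an arm reaches six, which happens only in a block of 12. A block of 12 has 12 / 7 = 1.714 such places. Three blocks, one of each size, hold 30 allocations, so the share is 1.714 / 30 = 5.7%, which simulation confirms. Correct guessing is the size-weighted mean of 66.6%, 65.3% and 64.3%: (8 × 66.6 + 10 × 65.3 + 12 × 64.3) / 30 = 65.3%. It is unchanged.

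**The case against.** The strongest reply is that one in six describes a perfectly informed observer. Recruitment runs over eight eight-hour shifts a week, and no text says that one person covers them, that a shared allocation log exists, or that recruiters are told the block size. Deferred baselines also break the link between recruitment order and allocation order. All of this stands, and it is why 16.7% is given as an upper bound.

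A reader might infer that recruiters can use predictions in choosing whom to approach. The documents do not support this. The AUDIT is completed after approach, only about 15% of those screened are expected to be positive, and the Human Subjects section says all eligible patients are approached. What remains is the effort put into trial consent once the cell is known.

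A reader might also infer that research staff see every assignment. That rests on the Brief Advice Condition and Potential Risks text, which other sections contradict.

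Nor is it right that analysis can do nothing. The Aim 1 model includes the baseline value of the outcome, and the general analytic approach adjusts for significant baseline differences. This deals with measured imbalance only.

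Finally, mixed blocks leave guessing near 65%, so block size is not the whole answer. That is correct, and it is a reason to add concealment. It is not a reason to keep the fixed size.

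**Conclusion.** The point holds as a minor design weakness that is almost free to improve. The plan fixes one block size, prints it in the protocol, and describes no means of keeping it from recruiters. Up to 16.7% of allocations (about 72 to 75 of 450) are determined by earlier ones for someone who knows the block size and the full history of the cell. The share is roughly 4% to 10% if 75% to 90% of that history is seen, and also lower while earlier recruits await baseline. Varying the size cuts the upper bound by about two thirds, to 5.7%.

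The documents show a risk. They do not show that selective enrolment occurred, and they suggest no motive or direction for it. Calling the whole trial unmasked would also go too far, since follow-up staff are to be blind. How far recruiters see allocations cannot be settled until the passages on who delivers BA are reconciled.

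**What to change.** 1. For any participants still to be randomized, replace the fixed block of 10 with sizes drawn at random, for example from 8, 10 and 12. The data manager holds the list, and neither the sizes nor the sequence is disclosed to recruiting staff.
2. Keep the list concealed from recruiters, because varying the size does not reduce guessing below about 65%. Remove the block details from documents they use.
3. Reconcile the passages on who delivers the BA session.
4. If enrolment is closed, report how allocation was concealed and describe the fixed block size as a limitation. The documents do not show whether enrolment is still open.

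The cost is a new list for the remaining participants. The mean block size stays at 10, and the largest possible imbalance from an unfinished block rises from 5 to 6 in each cell. Sample size and analysis are unaffected.

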Using the VA criteria for hiring and training peers, we expect that there will be a range of mental health conditions that peer mentors have dealt with in their lives. We will not exclude peers because of any conditions for which they are in stable recovery. Our priority will be to hire Veterans who are in long-term recovery. Because the peer mentors will work as part of the research team and will be supervised by the PI and the research coordinator, with support from other clinician investigators, we will have close monitoring of peer staff, as well as other staff, and are prepared to address any mental health and substance use issues that arise. If a peer is experiencing relapse, they will be assisted in seeking needed care and will not work with participants until they are stable. Also, if a peer relapses, participants will be reassigned to an alternative peer (supervised via weekly group supervision and bi-monthly individual supervision).

Follow-up Methods and Assessments. At the 3-, 6- and 12-month post-randomization follow-ups, participants will be called to complete a telephone follow-up survey. Participants may have the option to meet in person if necessary. The TLFB interview during follow-ups will be audio recorded. At enrollment, study staff will obtain consent, telephone numbers, and addresses, as well as information for contacts, at least one of whom does not live with the participant, who should know their whereabouts in the next 12 months. In addition, the following procedures will be implemented: 1) reminder calls/ letters will be started one month prior to each follow-up assessment until completed; 2) incentives will be given to participants who complete follow-ups ; and 3) participants will be encouraged to call the study office with any questions, and to notify us of address/telephone changes. A review article contains more detailed information regarding the follow-up protocol that will be used.⁶¹ Using these strategies, we typically achieve 12-month follow-up rates exceeding 80% at each assessment point.^{49,62,63}

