Measures (see Table 2 for measures and timing). The screen (~10 minutes) will be completed on paper by participants and will include demographics and the 10-item Alcohol Use Disorders Identification Test (AUDIT). Veterans screening positive on the AUDIT-C (4+ men/3+ women) will be consented to participate in the study. The baseline (~45 minutes) will be completed as an in-person interview in the ED and recorded on paper forms by RA. Participants may have the option to complete the baseline alone on paper-form or on the phone within up to two-weeks after enrollment, if necessary. Follow-up assessments will be completed over the phone (or in person if necessary) and responses will be entered into VA REDCap in real-time.

Screening Measure

The Mini-Cog assessment will be administered to all potential participants to detect cognitive impairment and inability to consent. A score of 3 or more will indicate no sign of cognitive impairment, therefore patient will be eligible for recruitment and screening.

Primary Outcome

Alcohol Consumption. We will administer a 30-day Timeline Follow-back (TLFB) for finer grained data (e.g., average consumption, percent days drinking, binge drinking days) (Hoeppner et al., 2010)⁹⁶

Secondary Outcomes

Alcohol Consumption: We will administer the AUDIT which includes the 3 questions of the AUDIT-C^{64,65,97} assessing alcohol consumption and binge drinking over the past 3-months, and 7 consequence questions, with established reliability and validity.^{65,66} In addition to standard item responses (e.g., categorical), we will enhance responses to obtain exact numbers for data analyses purposes to produce continuous response scales. Inclusion criteria are scores of 3+ for women and 4+ for men. A recent study validates the full AUDIT among Veterans, with scores of 14 and 10 (male, female, respectively) indicating an AUD.⁵⁶ However, to be inclusive, we will set the score for recommending specialty care conservatively at 10 for men and 8 for women.

Alcohol Consequences. The Short Index of Problems (SIP) will be used to assess drinking consequences with adequate reliability and validity.

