Self-Report Healthcare Service Use. We will use the Treatment Services Review (TSR) to measure health services use, which has adequate reliability and validity.⁷⁰ We will also access VHA electronic health data, focusing on primary care; substance abuse treatment, and psychiatric treatment services (including mutual aid groups such as AA, receiving detox services, and other substance abuse care settings).

Health Care Utilization using Medical Records. In the last year of the study, a review of participants' medical records will be conducted to determine diagnoses, service use (i.e., ED visits, hospitalizations, primary and specialty care) for one year pre- and post-entry into the study. We will use these data to assess agreement with self-report service use, particularly VHA services, and seek to understand sources of discrepancy. Data will be accessed through CPRS, Corporate Data Warehouse (CDW), and the Joint Legacy Viewer (JLV).

Health Functioning. One item from the SF-12⁷¹ will assess perceived health functioning, which are accepted

Table 2: Study Measures	Instrument	When*	#Min
Primary Outcomes			
Alcohol Consumption	TLFB	B, 3,6,12	20
Secondary Outcomes			
Alcohol Consumption	AUDIT	S, 3, 6, 12	5
Alcohol Consequences	SIP	B, 3, 6, 12	5
Health Service Use	TSR/CPRS	B, 3,6, 12	10-15
Health Functioning	SF-12	S, 3,6,12	
Depressive Symptoms	PHQ-9	B, 3,6,12	
PTSD Symptoms	PC-PTSD-5	B, 3,6,12	
Substance Use	ASSIST	B, 3, 6, 12	
Opioid Misuse	COMM	B, 3, 6, 12	
Problem Severity	BAM	B, 3,6,12	
Individual Factors			
Demographics	SAOM	S/B	5-10
Motivation to Change/Readiness	Rulers	B, 3, 6, 12	
Self-Efficacy	Ruler	B, 3, 6, 12	
Social Factors			
Social Support	mMOS	B, 3, 6, 12	10
Peers Services	WAI-SR	3	
Intervention Interaction	Metric, Sentiment		0

*S=Screen; B=Baseline, 3-month, 6-month, 12-month follow-ups

Veterans.²⁹

Substance Use

Alcohol, Smoking, and Substance Involvement Screening Test (ASSIST) is a structured interview for alcohol, tobacco, cannabis, stimulants, sedatives and opioid use disorders in general medical settings. We will use a brief screening for tobacco use (ASSIST-LITE) and the full ASSIST version 3 to measure use of all other substances.

Opioid Misuse: a modified version of the Current Opioid Misuse Measure (COMM) will assess extent of opioid medication misuse.

Individual Factors

Demographics: Background characteristics assessed include: age, sex, marital status, education, employment, income, legal history, deployment history, etc.⁷⁷

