outcomes for intervention studies.^{24,74}

Depressive Symptoms. The PHQ-9⁷⁵ will assess symptoms of depression (94% specificity, 99% sensitivity for current major depressive disorder), including suicidal ideation.

The Primary Care PTSD screening (PC-PTSD-5) is a 6-item self report measure that assesses Diagnostic and Statistical Manual of Mental Disorders, 5th Edition (DSM-5) symptoms of PTSD. The PC-PTSD-5 is currently used in VHA primary care clinics and has excellent internal consistency and is correlated with other PTSD measures.

Modified Brief Addiction Monitor (BAM). The Protective and Risk subscales of the BAM will be used and assesses severity of problems and can be used to measure change over time. The BAM has acceptable reliability and validity among

Motivation to Change / Readiness: Based on theory²³, we will assess readiness, intention, importance, and help seeking with visual analog rulers, which correlate with longer measures and predict outcomes.⁷⁹⁻⁸²

Self-efficacy. We will assess self-efficacy with a visual analog ruler.

Social Factors

Social Support. Social support will be assessed by the Modified Medical Outcomes Study (mMOS) Social Support Survey, a 8-item measure that assesses perceived social support, including emotional/informational, tangible, affectionate, and positive support. These subscales capture the domains of our theoretical model.

Peer Services. At the 3-month follow-up assessment we will use a the Working Alliance Inventory – short revised (WAI-SR) to assess satisfaction with services provided by peer support specialists.

Qualitative Interviews

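### The 3-month WAI-SR on peer services would largely reveal the arm to follow-up staff whom the plan calls blind, and nothing written protects the TLFB from this

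*Combined protocol and SAP*

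**What the plan says.** All references are to the combined protocol and SAP.

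- **Blinding.** Randomization Procedures: "Follow-up staff will be blind to condition".
- **Mode of follow-up.** Follow-up Methods and Assessments says that at 3, 6 and 12 months "participants will be called to complete a telephone follow-up survey", with an in-person option. Measures adds that "responses will be entered into VA REDCap in real-time".
- **Primary outcome.** Table 2 lists it as "Alcohol Consumption TLFB B, 3,6,12 20": a TLFB at baseline and at each follow-up, taking 20 minutes. It is an interview, and Follow-up Methods and Assessments states: "The TLFB interview during follow-ups will be audio recorded".
- **Peer-services measure.** Table 2 has "Peers Services WAI-SR 3", that is, at month 3 only. Measures, under Social Factors, gives its purpose: "to assess satisfaction with services provided by peer support specialists".
- **Who sees a peer.** Under Peer Mentor Content, peers give the APM arm its ED advice and up to six sessions over two months. Under Brief Advice Condition, BA participants are advised by a research assistant and have no sessions after the ED visit.
- **Prior peer services.** Both sets of exclusion criteria (screening and RCT) remove people with current peer services or peer services in the preceding three months.

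**The concern.** A questionnaire about a peer specialist applies, with few exceptions, to one arm only. If it is asked only of APM participants, its appearance in the call identifies the arm. If it is asked of everyone, the answers do. Either way, staff who are meant to be blind learn the allocation in a contact that also collects the primary outcome.

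Participants know what they received, so blinding of the follow-up staff is the only blinding the plan states. The TLFB is a recall interview in which the interviewer can probe more or less. An interviewer who knows the arm may, without intending it, probe differently. At stake is whether a between-arm difference in reported drinking can be presented as assessed blind.

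**Working it through.** **1. Does the text conflict with itself?**

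| Question | What the plan gives |
|---|---|
| Are follow-up staff blind? | Yes (Randomization Procedures) |
| Does the 3-month follow-up include the WAI-SR on peers? | Yes (Table 2; Social Factors) |
| Is the follow-up self-completed? | No: a staff call or visit with real-time entry (Follow-up Methods and Assessments; Measures) |
| Is the TLFB part of the same follow-up? | Yes, at 3, 6 and 12 months (Table 2) |
| Do both arms get study peers? | Not according to the arm descriptions (Peer Mentor Content; Brief Advice Condition) |
| Is the WAI-SR given by someone else, by self-completion, or after the TLFB? | Not stated anywhere |

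The APM sessions run for two months, so they are due to be over before the 3-month call, when the WAI-SR is asked.

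**2. Which TLFBs are exposed?**

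- Month 3: only if the WAI-SR comes before the TLFB. The order is not given.
- Months 6 and 12: if the same staff continue. Continuity is not given either.

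**3. The plan's own power figure.** Power and Sample Size Calculations expects 80% of 450 to be retained: 0.80 × 450 = 360, or 180 per arm. With two-sided α = 0.05 and d = 0.30:

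- SE of a standardised difference = √(2/180) = 0.1054
- 0.30 / 0.1054 = 2.846
- power ≈ Φ(2.846 − 1.960) = 0.81

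This agrees with the stated 80%. The power statement is not in dispute.

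**4. Illustration of what a small bias would do.** The documents give no bias figure, so the shifts b below are assumptions. With no true effect and an additive between-arm shift of b SD, the rejection rate is

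P(|Z + b/0.1054| > 1.96) = 1 − Φ(1.96 − b/0.1054) + Φ(−1.96 − b/0.1054).

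Data Analysis for Aim 1 estimates a time-averaged effect over three follow-ups. With equal visit weights, a shift at months 6 and 12 only moves the average by 2b/3.

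| Assumed shift per affected visit | All three visits | Months 6 and 12 only |
|---|---|---|
| 0.05 SD | b/SE = 0.474; 7.6% | 0.0333/0.1054 = 0.316; 6.2% |
| 0.10 SD | b/SE = 0.949; 15.8% | 0.0667/0.1054 = 0.632; 9.7% |

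For scale, 0.10 SD is one third of the d = 0.30 that the trial is powered to detect (0.10/0.30).

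The formula is a single two-group comparison. The planned model adjusts for baseline, averages over visits, and has a random effect for the peer or clinician. The first two would shrink the SE and raise these rates; the third would act the other way. The documents give no correlations from which to refine this.

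**The case against.** The strongest reply has five parts.

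- **The WAI-SR does not prove the arm.** The exclusions cover peer services before entry only, so a BA participant could later obtain VHA peer services outside the study. The text on ED advice is also uneven: Alcohol Brief Advice Content has the peer adding content to a pamphlet used in both arms, and the Human Subjects section has an ED clinician or peer mentor advising participants in both conditions. This stands. The arm would be revealed for nearly all participants, not all.
- **Nobody says the blinded interviewer asks it.** Participant Remuneration pays for the survey and the TLFB interview separately, so the two could be split between staff or ordered safely. That is possible, but no such arrangement is written, and the plan describes one group of follow-up staff as blind.
- **The TLFB is recorded.** Recordings would allow probing to be audited. This is at most a partial safeguard: no blinded audit or re-scoring is described, and a recording cannot undo uneven probing.
- **Other routes to unblinding exist.** The TSR service-use questions are asked at every follow-up, and participants may mention their peer. True, and moving the WAI-SR alone would not secure the blind. That is a reason to put the TLFB first, not a reason to leave an avoidable leak in the schedule.
- **The error rates are hypothetical.** Agreed. They show sensitivity to an assumed shift and nothing more.

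A reader might go further and infer that assessor blinding is certain to fail, or that the result will be biased towards APM. The documents do not support either: question order and staffing are unstated, and nothing gives the size or direction of any interviewer effect.

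**Conclusion.** The point holds. The plan claims blind follow-up staff and, in the same follow-up as the primary outcome, schedules an instrument that would tell them the arm for nearly everyone. No written step protects the TLFB at month 3 (if the WAI-SR comes first) or at months 6 and 12 (if the same staff continue).

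The size of any bias is unknown. Under assumed shifts of 0.05 to 0.10 SD with 180 per arm, a 5% false-positive rate becomes about 8% to 16% if all visits are affected, or about 6% to 10% if only months 6 and 12 are. The contradiction itself needs no such assumption. It rests on the arm descriptions under Peer Mentor Content and Brief Advice Condition being the operative ones.

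This should be corrected. It does not call the sample size or the analysis model into question.

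**What to change.** 1. At every follow-up, complete and save the TLFB first, ahead of the TSR service-use questions.
2. Take the WAI-SR out of the blinded interview. Collect it after the 3-month TLFB is saved, by self-completion or through existing study staff who are already unblinded, do not collect the TLFB and do not supervise the peers. Ratings gathered by the peers' own supervisor would invite favourable answers.
3. Have interviewers record any unblinding, and how it arose, at each follow-up.

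The cost is a change of order and mode for one short secondary instrument. WAI-SR completion may fall somewhat, particularly among participants who are hard to reach by mail or electronically, such as the homeless Veterans the trial deliberately includes.

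If the data are already collected, report who gave the WAI-SR and in what order relative to the TLFB, and qualify the claim of assessor blinding accordingly.
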